11.0 ADVERSE EVENT REPORTING

11.1 Leukemia-specific Adverse Event Recording and Reporting Guidelines

These guidelines serve to bring the Department of Leukemia in compliance with the institutional policy on Reporting of Serious Adverse Events.

Adverse event is any untoward medical occurrence that may present during treatment with a pharmaceutical product but which does not necessarily have a causal relationship with this treatment. Adverse drug reaction is a response to a drug which is noxious and unintended and which occurs at doses normally used in man for prophylaxis, diagnosis, or therapy of disease or for the modification of physiologic function.

Assessing causal connections between agents and disease is fundamental to the understanding of adverse drug reactions. In general, a drug may be considered a contributory cause of an adverse event if, had the drug not been administered, 1) the event would not have happened at all, 2) the event would have occurred later than it actually did, or 3) the event would have been less severe.

The Investigator or physician designee is responsible for verifying and providing source documentation for all adverse events and assigning the attribution for each event for all patients enrolled on the trial.

11.1.1 PDMS/CORe will be used as the electronic case report form for this protocol. Adverse events will be documented in the medical record and entered into PDMS/CORe.

11.1.2 These guidelines will be followed for the recording and reporting of adverse and serious adverse events.

- a. Baseline events will be recorded in the medical history section of the case report form and will include the terminology event name, grade, and start date of the event.
 - i. Baseline events are any medical condition, symptom, or clinically significant lab abnormality present before the informed consent is signed
 - a. Hematologic laboratory abnormalities will not be recorded as baseline events for patients with acute leukemia, myelodysplastic syndrome, chronic lymphocytic leukemia, or chronic myeloid leukemia in blast phase.
 - b. If exact start date is unknown, month and year or year may be used as the start date of the baseline event.
- b. The maximum grade of the adverse event will be captured per course or protocol defined visit date.
- c. These adverse events will be recorded in the case report form:
 - i. Any grade adverse event that is possibly, probably, or definitely related to the study drug(s).
 - ii. All serious adverse events regardless of attribution to the study drug(s).
 - iii. Any grade adverse event regardless of attribution to the study drug(s) that results in any dose modification.
- d. Hematologic adverse events will not be recorded or reported for studies in patients with acute leukemia, myelodysplastic syndrome, chronic lymphocytic leukemia, or chronic myeloid leukemia in blast phase except for:
 - i. Prolonged myelosuppression as defined by the NCI-CTCAE criteria specific for leukemia, e.g. marrow hypocellularity on day 42 or later (6 weeks) from start of therapy without evidence of leukemia (< 5% blasts), or that results in dose modifications, interruptions or meets the protocol definition of DLT or SAE.
- e. Serious adverse events will be reported according to institutional policy.
- f. Protocol specific language regarding the recording and reporting of adverse and serious adverse events will be followed in the event of discordance between the

protocol and Leukemia-specific adverse event recording and reporting guidelines.

11.1.3 Abnormal hematologic values will not be recorded on the case report form. For abnormal chemical values, the apogee or nadir (whichever is appropriate) will be reported per course on the case report form.

11.1.4 All events that are not listed as expected in section 11.1.2 will be collected for the purpose of grading, and determining attribution to study drug by the PI.

11.1.5 Serious Adverse Event Reporting (SAE)

An adverse event or suspected adverse reaction is considered “serious” if, in the view of either the investigator or the sponsor, it results in any of the following outcomes:

- Death
- A life-threatening adverse drug experience – any adverse experience that places the patient, in the view of the initial reporter, at immediate risk of death from the adverse experience as it occurred. It does not include an adverse experience that, had it occurred in a more severe form, might have caused death.
- Inpatient hospitalization or prolongation of existing hospitalization.
- A persistent or significant incapacity or substantial disruption of the ability to conduct normal life functions.
- A congenital anomaly/birth defect.

Important medical events that may not result in death, be life-threatening, or require hospitalization may be considered a serious adverse drug experience when, based upon appropriate medical judgment, they may jeopardize the patient or subject and may require medical or surgical intervention to prevent one of the outcomes listed in this definition. Examples of such medical events include allergic bronchospasm requiring intensive treatment in an emergency room or at home, blood dyscrasias or convulsions that do not result in inpatient hospitalization, or the development of drug dependency or drug abuse (21 CFR 312.32). Pregnancy, drug overdose, and secondary malignancy will be handled as SAE.

- Important medical events as defined above, may also be considered serious adverse events. Any important medical event can and should be reported as an SAE if deemed appropriate by the Principal Investigator or the IND Sponsor, IND Office.
- All events occurring during the conduct of a protocol and meeting the definition of a SAE must be reported to the IRB in accordance with the timeframes and procedures outlined in “The University of Texas M. D. Anderson Cancer Center Institutional Review Board Policy for Investigators on Reporting Unanticipated Adverse Events for Drugs and Devices”. Unless stated otherwise in the protocol, all SAEs, expected or unexpected, must be reported to the IND Office, regardless of attribution (within 5 working days of knowledge of the event).

"Serious Adverse Event Reporting (SAE) for M. D. Anderson-Sponsored IND Protocols":

2014-0933 Lirilumab and Rituximab for Relapsed/Refractory CLL

Version 2 – November 05, 2015

Page 19 of 27

- All life-threatening or fatal events, that are unexpected, and related to the study drug, must have a written report submitted within 24 hours (next working day) of knowledge of the event to the Safety Project Manager in the IND Office.
- Unless otherwise noted, the electronic SAE application (eSAE) will be utilized for safety reporting to the IND Office and MDACC IRB.
- Serious adverse events will be captured from the time of the first protocol-specific intervention, until 30 days after the last dose of drug, unless the participant withdraws consent. Serious adverse events must be followed until clinical recovery is complete and laboratory tests have returned to baseline, progression of the event has stabilized, or there has been acceptable resolution of the event.
- Additionally, any serious adverse events that occur after the 30 day time period that are related to the study treatment must be reported to the IND Office. This may include the development of a secondary malignancy.

Reporting to FDA:

- Serious adverse events will be forwarded to FDA by the IND Sponsor (Safety Project Manager IND Office) according to 21 CFR 312.32.

Investigator Communication with Supporting Companies:

- Any individual expedited SAE reports required by the FDA will be reported to BMS.
- **All Serious Adverse Events must be reported to BMS Worldwide Safety**
 - All SAEs, whether related or unrelated to lirilumab and all pregnancies must be reported to BMS (by the investigator or designee) within 24 hours.
 - All SAEs should be reported via confirmed facsimile (fax) transmission, or scanned and reported via electronic mail to:
 - SAE Email Address:** [contact]
 - SAE [contact]

12.0 DISCONTINUATION OF STUDY TREATMENT

A patient's treatment with study drugs may be discontinued for any of the following reasons:

- Clinically significant progressive disease
- Adverse events that are not manageable with dose adjustments and/or optimal medical management, or that, in the opinion of the investigator, pose an unacceptable risk for the patient.
- Investigator decision
- Patient decision (e.g., withdrawal of consent)
- Study termination by Sponsor

Patients who experience toxicity that can be clearly attributed to either lirilumab or rituximab may continue treatment with the other agent. If toxicity cannot be clearly attributed to a single agent, treatment with both agents should be discontinued. Patients who discontinue treatment for reasons other than progressive disease should remain on study and continue to have disease assessments per protocol.

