Patients who experience Grade 3 or 4 toxicity that can be clearly attributed to either lirilumab or to rituximab may continue treatment with the other agent while the causative agent is delayed until resolution of toxicity to grade \leq 1 or baseline. In cases where Grade 3 or 4 toxicity cannot be attributed to a specific study drug, both study drugs should be held regardless of attribution of toxicity until the toxicity is resolved to grade \leq 1 or baseline.

Rituximab and lirilumab administration should be delayed and increased monitoring of subjects should ensue if any of the following drug-related adverse event(s) occurs:

- Any Grade \geq 2 ALT, AST, or total bilirubin
- Any Grade \geq 2 non laboratory non-skin drug related adverse event except for fatigue
- Any Grade \geq 2 endocrine drug-related adverse event
- Any Grade \geq 3 skin drug related adverse event
- Any Grade \geq 3 drug-related laboratory abnormality (except lymphopenia or any electrolyte abnormality without any clinical sequelae that is either spontaneously reversible or resolves with clinical management to grade 2 or less within 72 hours)
- Any AE, laboratory abnormality or inter-current illness, which in the judgment of the investigator, warrants delaying the dose of study medication

Discontinuation of lirilumab will occur in the following situations:

- AST, ALT, or T Bili \geq Grade 3
- Grade 2 AST or ALT and symptomatic liver inflammation (e.g., right upper quadrant tenderness, jaundice)
- AST or ALT $>$ 3 x ULN and concurrent total bilirubin $>$ 2 x ULN in the absence of evidence of cholestasis (Hy's law)

CRITERIA FOR RESPONSE

Response will be assessed by the investigator, based on physical examinations, CT scans, laboratory results, and bone marrow examinations, based on the 2008 IWCLL criteria for response for CLL. Overall response (OR) includes complete remission (CR), CR with incomplete marrow recovery (CRi) or partial remission (PR) as determined by investigator assessment using CLL response criteria. Minimal residual disease (MRD) will be assessed in bone marrow by multi-color flow cytometry. Patients with missing or no response assessments will be classified as non-responders by intent to treat analysis.

Study Enrollment:

The study population for this research will consist of participants from:

Only at MDACC

Estimated Accrual:

Total Accrual at MDACC:	48
Estimated monthly accrual at MDACC:	1-2

Accrual Comments:

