6.0 DOSE DELAYS AND MODIFICATIONS

Patients who experience Grade 3 or 4 toxicity that can be clearly attributed to either lirilumab or to rituximab may continue treatment with the other agent while the causative agent is delayed until resolution of toxicity to grade ≤ 1 or baseline. In cases where Grade 3 or 4 toxicity cannot be attributed to a specific study drug, both study drugs should be held regardless of attribution of toxicity until the toxicity is resolved to grade ≤ 1 or baseline.

Rituximab and lirilumab administration should be delayed and increased monitoring of patients should ensue if any of the following drug-related adverse event(s) occurs:

- Any Grade ≥ 2 ALT, AST, or total bilirubin
- Any Grade ≥ 2 non laboratory non-skin drug related adverse event except for fatigue
- Any Grade ≥ 2 endocrine drug-related adverse event
- Any Grade ≥ 3 skin drug related adverse event
- Any Grade ≥ 3 drug-related laboratory abnormality (except lymphopenia or any electrolyte abnormality without any clinical sequelae that is either spontaneously reversible or resolves with clinical management to grade 2 or less within 72 hours)
- Any AE, laboratory abnormality or inter-current illness, which in the judgment of the investigator, warrants delaying the dose of study medication

Discontinuation of lirilumab will occur in the following situations:

- AST, ALT, or T Bili \geq Grade 3
- Grade 2 AST or ALT and symptomatic liver inflammation (e.g., right upper quadrant tenderness, jaundice)
- AST or ALT $> 3 \times$ ULN and concurrent total bilirubin $> 2 \times$ ULN in the absence of evidence of cholestasis (Hy's law)

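### For Grade 3-4 toxicity that cannot be attributed to one study drug, Section 6.0 holds both drugs until recovery and Section 12.0 discontinues both, so re-treatment is left undecided

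*Combined protocol and SAP*

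**What the plan says.** Section 6.0 (Dose Delays and Modifications), first paragraph, also printed in the abstract under the same title: "In cases where Grade 3 or 4 toxicity cannot be attributed to a specific study drug, both study drugs should be held". The hold runs until the toxicity has come down to grade 1 or less, or to baseline. If the event is clearly due to one drug, the patient "may continue treatment with the other agent while the causative agent is delayed".

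Section 6.0 then gives a list of drug-related events, introduced by: "Rituximab and lirilumab administration should be delayed and increased monitoring of patients should ensue if any of the following drug-related adverse event(s) occurs". One entry is "Any Grade ≥ 2 ALT, AST, or total bilirubin". A last list gives liver findings for which lirilumab is discontinued.

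Section 12.0 (Discontinuation of Study Treatment) opens with a list of reasons for which treatment *may* be discontinued. One reason begins: "Adverse events that are not manageable with dose adjustments and/or optimal medical management". A separate paragraph follows. It first says: "Patients who experience toxicity that can be clearly attributed to either lirilumab or rituximab may continue treatment with the other agent". It then says: "If toxicity cannot be clearly attributed to a single agent, treatment with both agents should be discontinued". Its last sentence keeps patients who stop for reasons other than progression on study, with disease assessments continuing.

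**The concern.** A Grade 3 or 4 event of unclear cause meets the condition of both rules. Under Section 6.0 the expected course is a pause and, on recovery, further treatment. Under Section 12.0 treatment with both drugs ends. Each rule is worded as a *should*, and neither mentions the other. An investigator could follow either section in good faith and reach the opposite decision on re-exposing a patient after a severe toxicity.

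The first stake is patient safety. The second is exposure: the primary endpoint is response during the first 6 months of therapy, and a patient who resumes may receive several more doses in that period than one who does not. Counts of treatment discontinuation would also depend on which section was followed.

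**Working it through.** **Step 1: the two rules side by side, for Grade 3-4 toxicity not attributable to one drug.**

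| Feature | Section 6.0 and abstract | Section 12.0 |
|---|---|---|
| Immediate action | both drugs stopped | both drugs stopped |
| Grade condition | Grade 3 or 4 | none stated |
| Condition for resuming | grade 1 or less, or baseline | none stated |
| Refers to the other section | no | no |

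The Section 6.0 wording is "both study drugs should be held regardless of attribution of toxicity until the toxicity is resolved". Holding and discontinuing are not used as synonyms: Section 6.0 itself keeps its delay rules apart from its list for discontinuing lirilumab, and the end of the Section 12.0 paragraph treats discontinuation as a lasting state.

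**Step 2: is there a rule of precedence?** None for dosing appears in the pages available for this review. The one discordance rule, Section 11.1.2 item f, concerns the recording and reporting of adverse events.

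**Step 3: difference in planned exposure, cycles 1-6.** From the table in Section 4.1:
- rituximab: 4 doses in cycle 1 + 5 (day 1 of cycles 2-6) = 9
- lirilumab: day 1 of cycles 1-6 = 6

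Difference = doses received under the hold rule minus doses received under the discontinue rule. The largest difference arises when recovery comes before the next planned dose, so that the hold costs nothing (9 rituximab and 6 lirilumab in all). Entries are rituximab/lirilumab.

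| Last dose before the event | Discontinue | Hold, no dose missed | Difference |
|---|---|---|---|
| C1D1 | 1/1 | 9/6 | 8/5 |
| C1D8 | 2/1 | 9/6 | 7/5 |
| C1D15 | 3/1 | 9/6 | 6/5 |
| C1D22 | 4/1 | 9/6 | 5/5 |
| C2D1 | 5/2 | 9/6 | 4/4 |
| C3D1 | 6/3 | 9/6 | 3/3 |
| C4D1 | 7/4 | 9/6 | 2/2 |
| C5D1 | 8/5 | 9/6 | 1/1 |
| C6D1 | 9/6 | 9/6 | 0/0 |

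If the toxicity does not resolve by the end of cycle 6, the two rules give the same exposure in those cycles. The range is therefore 0 to 8 rituximab and 0 to 5 lirilumab doses.

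**Step 4: a longer hold.** Assume a 28-day hold and missed doses not made up. Section 4.1 allows ±7 days on day 1 of cycles 2-12, so the result depends on whether the next day-1 dose is given inside its window.
- Event after C1D1: C1D8, C1D15 and C1D22 are missed. With C2D1 given, 6/6 − 1/1 = 5/5. With C2D1 skipped, 5/5 − 1/1 = 4/4.
- Event after C2D1: with C3D1 given, 9/6 − 5/2 = 4/4. With C3D1 skipped, 8/5 − 5/2 = 3/3.

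**Step 5: limits of the count.** Six cycles are 6 × 28 = 168 days, so C7D1 falls nominally on day 169. Counting 6 calendar months would bring in one more planned dose of each drug, and the extreme case would be 10/7 − 1/1 = 9/6. For Grade 3 or higher AST, ALT or bilirubin, Section 6.0 itself discontinues lirilumab, so there the open question concerns rituximab alone.

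**The case against.** The strongest reply is that Section 12.0 is the step after Section 6.0 has failed. Its title is about discontinuation, and its adverse-event reason presupposes that dose adjustment was tried. Read without that context, the disputed sentence would end both drugs even for a Grade 1 event of unclear cause, although the delay list in Section 6.0 generally starts at Grade 2. This makes the narrower reading plausible. It does not settle the matter: the limit sits in a separate list of reasons for which treatment may be stopped, and the sentence that says treatment should be stopped does not refer to it.

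It is also true that the study is single-centre with all dosing at that centre, so differences between sites do not arise, and that the investigator may always discontinue treatment. This reduces the practical risk but does not tell the investigator which section governs.

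A reader might draw four stronger conclusions that the documents do not support.
- *Section 6.0 contradicts itself for attributable events.* Its first paragraph permits the other drug to continue, and its delay list says both should be delayed for most of the same events. Delaying both satisfies both clauses. For Grade 3 or higher drug-related liver tests, discontinuing lirilumab and delaying rituximab satisfies all three parts. This is a point of clarity only.
- *The conflict changes which hematologic events are recorded.* Section 11.1.2 item d includes events that lead to dose interruption. Both rules interrupt dosing, so recording does not depend on the choice.
- *The number of affected patients can be scaled from the earlier lirilumab trials in Section 2.5.* The two with related-event counts that might be used are a monotherapy trial and a blinded trial of lirilumab or placebo. Attribution between lirilumab and rituximab cannot arise in either.
- *The toxicity monitoring is affected.* Section 14.0 defines toxicity by grade, non-hematological type and relatedness, not by the dosing action.

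**Conclusion.** The conflict stands for one situation: Grade 3-4 toxicity not attributable to a single drug. The text gives two answers on whether treatment may resume, and a plausible but unwritten limit on Section 12.0 is the only way to reconcile them. The mismatch in wording is certain; whether Section 12.0 was meant to reach these events at all is not.

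Per affected patient the difference in cycles 1-6 is at most 8 rituximab and 5 lirilumab doses. That maximum needs an event after the first dose that resolves before C1D8; later events or longer holds give less, down to zero. The counts assume that missed doses are not made up, which the protocol does not address. Frequency cannot be sized. No stated statistical figure changes, and disease assessments continue after discontinuation. The point is worth fixing because it concerns re-treatment after severe toxicity, not because it alters the design's statistical properties.

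**What to change.** Reconcile the abstract, Section 6.0 and Section 12.0 so that toxicity not attributable to one drug leads to one stated action for each grade. State whether the attribution sentences in Section 12.0 apply only to permanent discontinuation, and add cross-references between Sections 6.0 and 12.0. In the same edit, say how the first paragraph of Section 6.0 and its delay list relate. Which action applies is for the clinical team to decide.

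The cost is amendment wording only; no sample size, boundary or analysis has to be redone. The abstract page marks this version as terminated, so new wording can no longer guide dosing under it. The sponsor can still record which rule was applied when exposure and discontinuations are reported.

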13.0 CORRELATIVE STUDIES

Correlative studies relating to immunologic response will be collected on a separate IRB-approved Protocol (PA13-0291).

Approximately 20cc of peripheral blood will be collected at the following time-points (pretreatment, C1D1, C1D8, C2-24D1) and stored in the Leukemia Research Bank. This testing is optional and failure to collect these studies at any of the specified time-points is not a protocol deviation. Approximately 3cc of bone marrow aspirate will be collected at the following time-points (pretreatment, after C3, after C6, after C9, after C12, after C15, after C18, after C21, after C24) and stored in the Leukemia Research Bank. This testing is optional and failure to collect these studies at any of the specified time-points is not a protocol deviation.

Immune Function Studies ([name] [name], MDACC) – This testing is optional and failure to collect these studies at any of the specified time-points is not a protocol deviation. We use 14 color multiparameter flow cytometry to comprehensively analyze NK cell frequencies, phenotype, function (both KIR-ligand mediated and ADCC), homing to sites of tumor (bone marrow and lymph node where available) using the assays described below and in table below. PBMC will be collected on Day 1 (prior to the study drugs) and Day 2 of each cycle (cycles 1-12). In addition, PBMC will be collected on day 8 of cycle 1. Approximately 3cc of bone marrow aspirate will be collected at the following time-points (pretreatment, after C3, after C6, after C9, after C12). To determine whether treatment with a combination of rituximab and lirilumab will enhance CD16 mediated ADCC, NK cells will be stimulated with antibodies against CD20 (Rituximab) to trigger ADCC responses against CD20+ cell lines (Raji and Daudi), in the presence or absence of lirilumab. Function will be assessed using a combination of degranulation (CD107a), effector cytokine production (IFN- γ and TNF- α) and 51chromium release. Each patient will be used as his / her own control and the effect of rituximab and lirilumab combination therapy on NK cell frequency, phenotype and function will be assessed longitudinally. A total of 25 samples will be analyzed per patient. Samples will be sent to the laboratory of [name], MDACC.

Table 13.1. Flow cytometric parameters that will be used to evaluate the impact of rituximab + lirilumab on NK cell phenotype and function

Cell type	Markers & transcription factors	Effector molecules
NK cells	CD45 ⁺ CD56 ⁺ CD3 ⁻ NKp46 ⁺ IL-2R α ^{+/-} IL-12R β ⁺ IL-15R β ^{+/-} IL-18R ⁺ T-bet ^{+ or -} Eomes ^{+ or -}	Perforin, Granzymes, TNF α , INF γ Cytotoxicity CD107a
NK subsets (may be + or -)	CD16, CD27, CD57, CD94, CD141, CD161, KLRG-1, 2B4, 4-1BB, NKG2A, -C, -D, DNAM-1, NKp30, NKp44, KIRs, CD132	
NK activation markers	CD25, CD69, down-regulation of CD27 & KLRG-1, Ki67, Lag3, CD107a	
KIR receptors	KIR2DL1 (clone 143211, KIR2DS1 (clone 11PB6), KIR2DL3 (clone REA147), KIR2DSL2/3 (clone GL183), KIR3DL1 (clone DX9), KIR3DSL11 (CLONE z27.3.7)	
Adhesion / migration	CX3CR1, CCR9, α 4 β 7, CD62L, CCR7, CCR8, CXCR3, CLA	
Costimulatory molecules	PD1, PDL1, PDL2, Lag 3 (to assess exhaustion)	

